## **8. REGULATORY ISSUES**

### **8.1 ETHICS APPROVAL**

The Study Coordination Centre has obtained approval from the by the North of Scotland (1) Research Ethics Committee and Health Research Authority (HRA). The study must also receive confirmation of capacity and capability from each participating NHS Trust before accepting participants into the study or any research activity is carried out. The study will be conducted in accordance with the recommendations for physicians involved in research on

human participants adopted by the 18th World Medical Assembly, Helsinki 1964 and later revisions.

## **8.2 CONSENT**

Consent to enter the study must be sought from each participant only after a full explanation has been given, an information leaflet offered and time allowed for consideration. Signed participant consent should be obtained. The right of the participant to refuse to participate without giving reasons must be respected. After the participant has entered the study the clinician remains free to give alternative treatment to that specified in the protocol at any stage if he/she feels it is in the participant's best interest, but the reasons for doing so should be recorded. In these cases the participants remain within the study for the purposes of follow-up and data analysis. All participants are free to withdraw at any time from the protocol treatment without giving reasons and without prejudicing further treatment.

## **8.3 CONFIDENTIALITY OF RECORDS:**

The Chief Investigator will preserve the confidentiality of participants taking part in the study and is registered under the Data Protection Act. All data will be analysed pseudoanonymously.

## **8.4 INDEMNITY**

Imperial College London hold negligent harm and non-negligent harm insurance policies which apply to this study.

## **8.5 SPONSOR**

Imperial College London will act as the main Sponsor for this study. Delegated responsibilities will be assigned to the NHS trusts taking part in this study.

## **8.6 FUNDING**

The Imperial Biomedical Research Centre and British Heart Foundation are funding this study.

## **8.7 AUDITS**

The study may be subject to inspection and audit by Imperial College London under their remit as sponsor and other regulatory bodies to ensure adherence to GCP and the UK Policy Framework for Health and Social Care Research

## **9. STUDY MANAGEMENT**

The day-to-day management of the study will be co-ordinated by [name].

## **10. PUBLICATION POLICY**

Our aim to publish in a major international cardiology journal and present at international cardiology conferences.

## 12. APPENDICES

### Appendix 1 – Arrhythmic syndromes

#### Group B (concealed arrhythmia syndromes):

- Concealed Brugada syndrome
- Early repolarisation syndrome
- Idiopathic VF
- Purkinje-related arrhythmic syndrome
- Concealed pre-excitation

#### Group C (manifest arrhythmia syndromes):

- Manifest Brugada syndrome
- Manifest Long QT syndrome
- Manifest short QT syndrome
- Manifest pre-excitation / Wolff-Parkinson-White syndrome

- Catecholaminergic polymorphic VT (CPVT)
- Arrhythmic cardiomyopathy (ACM)
- Arrhythmogenic right ventricular cardiomyopathy (ARVC)
- Arrhythmogenic left ventricular cardiomyopathy (ALVC)
- Hypertrophic cardiomyopathy
- Dilated cardiomyopathy
- Hypokinetic non-dilated cardiomyopathy
- Lamin-related cardiomyopathy
- Desmoplakin-related cardiomyopathy
- Titin-related cardiomyopathy
- Filamin C-related cardiomyopathy

#### Appendix 2 – ECG AI algorithms / neural networks that will be developed

- NN1 - Direct classification of the Brugada ECG pattern: This neural network will be trained to output whether a Brugada ECG pattern is detected based on the expert consensus classification. We will pool phenotype positive Brugada ECGs and non-Brugada ECGs within our ECG dataset.
- NN2 - Measurement-based classification of the Brugada ECG pattern: This neural network will be trained to establish the beta angle of the QRS (between the upslope of the S wave and downslope of the R' wave). The beta angle can be used to discriminate the Brugada pattern from Brugada mimics. Experts will be tasked with performing manual measurements on the ECG and the consensus measurement will be used. We will pool ECGs from all 3 groups within our ECG dataset.
- NN3 - Deep learning of concealed Brugada syndrome: This neural network will be trained to output whether an ECG represents underlying concealed Brugada syndrome. We will pool phenotype negative Brugada ECGs with a confirmed clinical diagnosis of Brugada syndrome alongside non-Brugada ECGs within our ECG dataset.
- NN4 - Deep learning of an SCN5a mutation from the 12-lead ECG: This neural network will be trained to detect changes in the ECG which indicate an underlying SCN5a mutation. In ECGs for patients who have already had SCN5a genetic testing, these ECGs will be divided into two groups based on their SCN5a status and used to train the neural network.

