## **3.3 METHODOLOGY**

### **Study A: Brugada ECG AI development**

The research team will collate at least 3000 ECGs, representing the 3 different categories previously mentioned. All ECGs will be either digital or converted to a digital format using in-house developed software. ECGs will subsequently be processed to enable direct extraction of the ECG complexes from the recordings. The resulting ECG data will be segmented to enable labelling by experts in Brugada ECG analysis.

The anonymous ECG data will be reviewed and annotated by experts. Each ECG will be labelled by 5 individual experts from a larger pool of experts, who will collectively share the task of ECG labelling for our entire training set. Experts will be comprised from the ICC specialists at Imperial College Healthcare NHS Trust, as well as our research collaborators within the UK and internationally. The categorisation of each case will be determined by expert majority agreement.

The labelled ECG data will be divided into the training set (75% of ECG data) and a separate hold-out validation set (25% of ECG data). The training set will be used to train separate neural networks (Appendix 2). Once the neural networks have been developed, they will be tested for their accuracy against a hold-out validation dataset.

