### Application of ECG AI to ECG recordings

ECG recordings will be downloaded onto local storage. The digital ECGs will be processed and denoised using specialized algorithms developed by the research team. The previously developed ECG AI algorithms for Brugada syndrome will subsequently be applied to the cleaned ECG recordings for all patient groups.

We will establish the sensitivity for the Brugada classification algorithms on recordings from patients with manifest Brugada syndrome (Group C) and their specificity using the recordings from the healthy volunteers (Group A). The algorithms will also be applied to

patients with concealed arrhythmia syndromes (Group B) to determine the diagnostic yield of different ambulatory ECG recording modalities for different time durations. We will apply both the in-house developed Brugada ECG AI algorithms as well as existing ECG AI algorithms developed by external academic or industry collaborators, to investigate for underlying concealed arrhythmias.

**Commented [BK2]:** From this description I think this should be a Pre-clinical device development or performance testing medical device study (no MHRA review required)

**Commented [KS3R2]:** I have amended project filter q2 on IRAS to reflect

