#### Primary Outcome Measures

- Sensitivity, specificity and AUC value for neural networks 1 and 2 to detect the Brugada ECG pattern in 12-lead ECGs.

- Yield of extended duration ambulatory ECG monitoring to detect the Brugada ECG pattern in patients with concealed Brugada syndrome, using neural networks 1 and 2.
- Sensitivity, specificity and AUC value for neural network 3 to diagnose concealed Brugada syndrome from 12-lead ECGs
- Sensitivity, specificity and AUC value for neural network 4 to diagnose an SCN5a mutation from 12-lead ECGs.
- Yield of extended duration ambulatory ECG monitoring to detect the Brugada ECG pattern (neural networks 1 and 2) and LQTS manifestation in patients with idiopathic VF.

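### Network 1 is trained without pattern-absent ECGs from Brugada patients, so its specificity is not shown to hold in the concealed Brugada group whose primary yield it helps to read

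*Protocol*

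**What the plan says.** Appendix 2 of the protocol defines the ECG pool for each network.

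- **NN1** is trained to report whether the Brugada pattern is present, against the expert consensus label: "We will pool phenotype positive Brugada ECGs and non-Brugada ECGs within our ECG dataset".
- **NN2** works through the beta angle: "We will pool ECGs from all 3 groups within our ECG dataset".
- **NN3** looks for concealed disease: "We will pool phenotype negative Brugada ECGs with a confirmed clinical diagnosis of Brugada syndrome alongside non-Brugada ECGs within our ECG dataset".

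Study A (section 3.3) describes the collected ECGs as "representing the 3 different categories previously mentioned". It divides the labelled data 75% to training and 25% to hold-out, with no separate description for any one network.

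Section 3.4 lists as a primary outcome the yield of extended monitoring "to detect the Brugada ECG pattern in patients with concealed Brugada syndrome, using neural networks 1 and 2". It does not say how the two networks' readings are combined.

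The Study Summary defines Group B as patients with a normal ECG and a known arrhythmic diagnosis, and Appendix 1 places concealed Brugada syndrome in that group. Under the application of ECG AI to recordings (section 3.3), sensitivity on ambulatory recordings is taken from manifest Brugada patients in Group C and specificity from the healthy volunteers in Group A. The algorithms are then applied to Group B.

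**The concern.** In concealed Brugada patients, NN1 has to tell apart two states of the same kind of patient: pattern present now, and pattern absent now. Its training pool poses a different contrast. Every positive is a Brugada patient showing the pattern, and every negative is an ECG from outside Brugada syndrome. Pattern and disease are confounded, and the network sees no counter-example that would teach it to ignore features of the disease that remain when the pattern is absent.

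NN3 exists because the investigators think such features may be learnable. If they are, NN1 may pick up some of them and call a baseline ECG positive. That call would enter the primary yield as an unmasked pattern. The absolute yield in concealed Brugada syndrome could then be biased, and nothing the protocol commits to reporting would show by how much.

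**Working it through.** **Which ECG classes each step uses**

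| Step | Pattern-positive Brugada | Pattern-absent Brugada | Non-Brugada |
|---|---|---|---|
| NN1 pool (Appendix 2) | yes | not listed | yes |
| NN2 pool (Appendix 2) | yes | yes | yes |
| NN3 pool (Appendix 2) | not listed | yes | yes |
| Hold-out (section 3.3, Study A) | 25% of all labelled data; composition for NN1 not stated | same | same |
| Ambulatory accuracy (section 3.3) | Group C, sensitivity | none | Group A, specificity |
| Primary yield, NN1 and NN2 (section 3.4) | to be detected | baseline state | – |

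The pattern-absent Brugada column is empty for NN1's training pool and for ambulatory specificity. It is the baseline state of the patients in the primary yield.

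**The plan's own figure**

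Inputs from section 7: 25% sensitivity for 24-hour Holter, 60% for prolonged recording, 80% of Holter-positive cases also found by prolonged recording, 90% power, 5% significance (two-sided assumed).

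- Holter only: 0.25 × (1 − 0.80) = 0.05
- Prolonged only: 0.60 − 0.25 × 0.80 = 0.40
- Sum s = 0.45; difference d = 0.35
- n = (1.960 × √0.45 + 1.282 × √(0.45 − 0.35²))² / 0.35² = 34.2, rounded up to 35

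The stated 35 patients reproduces. The sample-size arithmetic is not in question.

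**Effect on the absolute yield**

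Let y be the true yield and f the proportion of pattern-absent concealed Brugada patients whom NN1 flags, with an NN1 positive counting towards yield. Then

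apparent yield = y + (1 − y) × f

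The protocol gives no f. Values of 10% and 20% are assumed for illustration.

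| True yield | f = 10% | f = 20% |
|---|---|---|
| 25% | 0.25 + 0.75 × 0.10 = 32.5% | 0.25 + 0.75 × 0.20 = 40% |
| 60% | 0.60 + 0.40 × 0.10 = 64% | 0.60 + 0.40 × 0.20 = 68% |

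A smaller assumed f has a smaller effect: at 1%, 25% reads 25.8% and 60% reads 60.4%.

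**Effect on the paired comparison**

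If the feature that triggers the flag is persistent, the same patients are flagged on both recordings, with the same f:

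- f = 10%: 64 − 32.5 = 31.5 points
- f = 20%: 68 − 40 = 28 points
- Planned difference: 60 − 25 = 35 points

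Persistent flags shrink the difference by the factor (1 − f). They do not create one.

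**Errors in the other direction**

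If NN1 also misses a proportion m of true patterns, the apparent yield is y(1 − m) + (1 − y)f. The two errors cancel when m = (1 − y)f / y. At f = 10% this is 0.075 / 0.25 = 30% for a true 25%, and 0.04 / 0.60 = 6.7% for a true 60%. The net direction of the bias is therefore not fixed.

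**The case against.** Several points on the other side stand.

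- **The hold-out.** A reader might infer that NN1 will be tested only on the two classes in its pool. The protocol does not say so. Study A splits the whole labelled dataset, and Appendix 2 describes pools without giving NN1 its own hold-out. The hold-out may contain pattern-absent Brugada ECGs; what is missing is any statement that it does, or that specificity will be reported for them.
- **Known failure.** A reader might infer that NN1 will misread concealed Brugada ECGs. Nothing shows that. These ECGs are normal by the protocol's definition and could be easier negatives than the Brugada mimics mentioned under NN2, NN1's target is the expert pattern label, and NN3's premise is a hypothesis still to be tested.
- **A false gain from long monitoring.** A persistent feature would be flagged on both recordings, so those pairs are concordant in McNemar's test. Sporadic false alarms accumulating over up to 3 months could widen the difference, but that is a different mechanism. The protocol gives no rate for it, and changing NN1's pool might not cure it.
- **NN2.** It also reads the yield and does pool all three groups. The gap concerns NN1 and any rule under which an NN1 positive counts.

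Two further replies carry less weight. The term non-Brugada might mean any ECG without the pattern, but the NN3 entry sets phenotype-negative Brugada ECGs beside non-Brugada ECGs as a separate class. The continuous recordings and the index 12-lead ECG would let the team separate persistent from transient calls, but the protocol does not prescribe that check. The manual review it does plan covers stressor periods and is not described as confirming network calls.

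**Conclusion.** The point holds as a mismatch between how NN1 is built and where it is used. Its accuracy is not shown to apply to pattern-absent ECGs from Brugada patients, and the absolute primary yield can be biased as a result. At an assumed f of 10–20%, the upward bias is 7.5 to 15 points on a true 25% and 4 to 8 points on a true 60%. These figures assume that an NN1 positive is enough to count and that no true patterns are missed. The documents support neither a value of f nor a net direction.

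It would go too far to conclude that the primary question is left unanswered. The 35-patient calculation is sound on its own inputs, and the persistent-feature mechanism works against the planned Holter versus prolonged comparison. This is a cheap improvement, best made before NN1 is trained.

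**What to change.** Change the NN1 entry in Appendix 2 so that it pools all three ECG groups, as the NN2 entry does. Code ECGs from confirmed Brugada patients that the experts label as pattern-absent as negatives, in both training and hold-out. In the first primary outcome of section 3.4, report NN1's specificity separately for phenotype-negative Brugada ECGs and for non-Brugada ECGs.

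The cost is small. The ECGs are already to be collected and reviewed by the experts for Study A, and NN2 and NN3 use them. The downside is that NN1's headline specificity and AUC may look slightly less favourable. In return, the specificity reported for NN1 would cover the kind of ECG on which the concealed Brugada yield depends.

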## STUDY SUMMARY

TITLE	Unmasking Concealed Arrhythmia Syndromes
DESIGN	Proof-of-concept studies to develop ECG AI algorithms, followed by case-control diagnostic accuracy study and prospective cohort studies
AIMS	
 
1. To develop machine learning algorithms for 12-lead ECGs to detect diagnostic features of Brugada syndrome.
 
2. To test and validate these algorithms prospectively in participants wearing ambulatory ECG recording devices.
 
3. To ascertain the role of UHF-ECG for risk stratification in patients with inherited arrhythmogenic conditions
 

OUTCOME MEASURES	
 
• Brugada ECG algorithm sensitivity, specificity and AUC value for both 12 lead ECGs and 12 lead vest ECGs
 
• Yield of extended duration multi-electrode ambulatory ECG monitoring to detect the Brugada ECG pattern in concealed Brugada syndrome
 
• The utility of extended duration multi-electrode ambulatory ECG monitoring to detect a single case of underlying Brugada or LQTS manifestation in idiopathic VF
 

POPULATION	Healthy volunteer controls, patients with a diagnosis of Brugada syndrome, patients with a diagnosis of idiopathic VF syndrome and patients with other inherited arrhythmogenic conditions
ELIGIBILITY	
Participant sets (Appendix 1):
 
 
• Group A – healthy volunteers
 
• Group B – concealed arrhythmia syndrome patients (patients with a normal ECG with a known underlying arrhythmic diagnosis)
 
• Group C – manifest arrhythmia syndrome patients (patients with an arrhythmic syndrome with an abnormal ECG)
 

DURATION	November 2023 – November 2026 (3 years)

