## **7. STATISTICS AND DATA ANALYSIS**

We expect to have access to over 3000 patients' worth of ECG data to train and validate our neural networks, comprising a similar proportion of Brugada and non-Brugada ECGs. Our group has published extensively regarding applications of AI to ECG data (13–17) and includes experienced, independently-funded clinician scientists and engineers with expertise in machine learning. They will guide me in developing neural networks for ECG classification tasks and signal processing. As we will be employing a very similar methodology to our previous successful ECG AI projects in this experiment, we are confident that this quantity of ECG data will be sufficient to develop highly accurate neural networks.

The accuracy of the prolonged duration ambulatory ECG recordings will be calculated using a binomial distribution. Assuming an actual accuracy of 95% and a target accuracy of >85% for ECG analysis discriminating between healthy normal participants and manifest Brugada patients, 90 patients will provide greater than 80% power in demonstrating that the measured accuracy is significantly greater than 85% at the two-tailed 5% significance level. To achieve 90 patients with some loss to follow up, I will recruit 50 healthy volunteers and 50 manifest Brugada patients.

McNemar's test will be used for paired analysis of 24-hour 12 lead Holter and prolonged ambulatory ECG recordings in the concealed arrhythmia patient set. Historical data report 20 to 34% sensitivity for 24-hour Holter for detection of the Brugada ECG pattern in patients with concealed Brugada syndrome (5,6). Assuming 25% sensitivity for 24-hour Holter and 60% for prolonged ambulatory ECG recordings beyond 24 hours, with the prolonged ambulatory ECG recordings being able to identify 80% of 24-hour Holter-identified cases, 35 patients would be needed to provide 90% power at the 5% significance level. I will recruit 50 patients.

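### NN3's positives are chosen for lacking the Brugada pattern but its negatives are not matched on ECG appearance, so its primary specificity and AUC depend on an unstated case mix

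*Protocol*

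**What the plan says.** Appendix 2 states NN3's task as "This neural network will be trained to output whether an ECG represents underlying concealed Brugada syndrome" and its data as "We will pool phenotype negative Brugada ECGs with a confirmed clinical diagnosis of Brugada syndrome alongside non-Brugada ECGs within our ECG dataset". For NN1, the network that classifies the Brugada pattern itself, the data are "We will pool phenotype positive Brugada ECGs and non-Brugada ECGs within our ECG dataset". The negative class has the same wording in both entries, and neither entry restricts it by ECG appearance. NN2 pools all three groups of the dataset to estimate the beta angle, and its entry adds: "The beta angle can be used to discriminate the Brugada pattern from Brugada mimics".

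On the make-up of the dataset, Study A in section 3.3 says: "The research team will collate at least 3000 ECGs, representing the 3 different categories previously mentioned". Section 7 describes it as "comprising a similar proportion of Brugada and non-Brugada ECGs". Neither splits the non-Brugada ECGs into normal and abnormal. Study A divides the labelled data into 75% for training and 25% for hold-out validation.

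Section 3.4 lists among the primary outcomes "Sensitivity, specificity and AUC value for neural network 3 to diagnose concealed Brugada syndrome from 12-lead ECGs". The Study Summary describes Group B as "concealed arrhythmia syndrome patients (patients with a normal ECG with a known underlying arrhythmic diagnosis".

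**The concern.** A classifier learns whatever separates the two classes it is given. NN3's positives all lack the visible Brugada pattern. If some of its negatives are visibly abnormal for other reasons, the network can reject those on their abnormality alone, without learning anything about concealed Brugada syndrome. Each such ECG would still count as a correct negative in specificity and AUC.

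The question that matters for NN3 is narrower: among people whose ECG looks normal, can it tell those with Brugada syndrome from those without? The pooled comparison answers a different question, and the answer moves with the case mix. The hold-out set does not guard against this, because it is cut from the same labelled data and carries the same mix. A network trained on an unsuitable contrast also cannot be fully repaired at analysis, so the class definition in Appendix 2 matters before training starts.

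**Working it through.** **Step 1. Is the negative class restricted anywhere?** Setting the places side by side:

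- Appendix 2, NN3: positives are restricted to phenotype-negative ECGs; negatives have no restriction.
- Appendix 2, NN1: the same negative class, in the same words.
- Section 3.1, Brugada ECG AI training: the sources are ECGs of patients with established Brugada syndrome, plus ECGs of host-trust patients with no ECG criterion stated.
- Section 3.3, Study A: three categories said to have been mentioned before. The three-way scheme set out before that point is Groups A to C (Study Summary; section 3.1). Group C is defined by an abnormal ECG, and Appendix 1 lists in it manifest long QT syndrome, pre-excitation and several cardiomyopathies, none of which is Brugada syndrome.

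On that reading the non-Brugada pool contains visibly abnormal ECGs. The alternative reading of the three categories is pattern-positive Brugada, pattern-negative Brugada and non-Brugada. It leaves the make-up of the last category open, and the mention of mimics under NN2 suggests that abnormal ECGs would be in it. Neither reading restricts NN3's negatives to normal ECGs.

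**Step 2. Is there a planned figure to reproduce?** No. The protocol gives no target, expected value or sample size for NN3's specificity or AUC. Section 7 gives about 3000 ECGs, roughly half of them non-Brugada, so the hold-out has about 0.25 × 3000 = 750 ECGs, of which about 375 are non-Brugada. How those 375 divide into normal and abnormal is not stated.

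**Step 3. How does the mix enter the result?** Let f be the share of negatives that are visibly abnormal. AUC is the probability that a random positive scores above a random negative. A random negative is normal with probability 1 − f and abnormal with probability f. So, for a given trained network,

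AUC(pooled) = (1 − f) × AUC(normal) + f × AUC(abnormal).

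Specificity at a fixed threshold follows the same formula. The shift from the normal-only value is f × [AUC(abnormal) − AUC(normal)]. Its size depends on f, and its sign on which negatives are harder.

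**Step 4. Illustration.** Every component value here is an assumption; the protocol gives none. AUC against normal negatives is set at 0.70.

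| AUC against abnormal negatives | f = 0 | f = 25% | f = 50% |
|---|---|---|---|
| 0.95 (easy to reject) | 0.70 | 0.75 × 0.70 + 0.25 × 0.95 = 0.7625 | 0.50 × 0.70 + 0.50 × 0.95 = 0.825 |
| 0.70 (equally hard) | 0.70 | 0.70 | 0.70 |
| 0.55 (harder, mimic-like) | 0.70 | 0.75 × 0.70 + 0.25 × 0.55 = 0.6625 | 0.50 × 0.70 + 0.50 × 0.55 = 0.625 |

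For specificity, with an assumed 0.70 against normal negatives and 0.98 against easy abnormal ones, the pooled value is 0.75 × 0.70 + 0.25 × 0.98 = 0.77 at f = 25% and 0.50 × 0.70 + 0.50 × 0.98 = 0.84 at f = 50%. With 0.50 against harder ones it is 0.50 × 0.70 + 0.50 × 0.50 = 0.60 at f = 50%.

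**The case against.** The strongest reply is that the protocol never says the pool contains abnormal ECGs. Groups A to C are the sets for the prospective studies, whereas Study A uses separate, retrospectively collated ECGs, and the three categories are not defined for that dataset. This is correct as far as it goes. It means that f is unknown, not that f is zero, and an undefined negative class is itself the difficulty.

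A reader might infer that NN3's specificity and AUC are inflated. The documents do not support that. Inflation needs abnormal negatives that are present and easier to reject than normal ones. Mimic-like negatives could pull the figures down, as the last row of the table shows.

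A reader might also infer that a single pool cannot serve both NN1 and NN3. That too goes beyond the text: a mixed pool can serve both if each network's classes are defined and results are reported by stratum.

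A further fair point is that phenotype-negative means without the Brugada pattern, not necessarily normal in every other respect. Restricting only the negatives to normal ECGs could then create the opposite shortcut, with any abnormality read as concealed Brugada. This stands, and it is why the criterion must apply to both classes.

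Finally, Study B takes specificity from healthy volunteers, whose hearts are checked by echocardiogram. That is a normal comparator, but it concerns ambulatory recordings and is paired with sensitivity in manifest Brugada patients. It does not supply the missing comparison for NN3 on 12-lead ECGs.

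**Conclusion.** The point holds in limited form. Appendix 2 selects NN3's positives on ECG appearance and leaves its negatives unmatched, so a primary outcome depends on a case mix that the protocol does not state. Whatever the direction, the reported specificity and AUC cannot be taken as discrimination among normal-looking ECGs. Upward bias is plausible but not shown: on the assumed values, a normal-only AUC of 0.70 could appear as anything from 0.625 to 0.825 at a 50% share of abnormal negatives. If the pool held no abnormal ECGs, or if they were exactly as hard to reject as normal ones, there would be no shift.

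This rests on reading the three categories as Groups A to C or, failing that, on the absence of any restriction. It is not merely a detail for an analysis plan, because Appendix 2 itself sets the classes on which the network is trained. It should be put right before training but is not of the highest severity: Study A is proof-of-concept work, no sample size or success threshold rests on NN3, and the primary ambulatory yields use NN1 and NN2.

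**What to change.** In Appendix 2, define the non-Brugada class separately for each network.

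- **NN3:** make the primary training and hold-out comparison like for like. Apply the same expert-read normal-ECG criterion to the concealed-Brugada positives and to the non-Brugada negatives. Report results on the remaining ECGs separately.
- **NN1 and the NN2-based classification:** keep the broader pool, and report hold-out specificity separately for normal and for abnormal or mimic non-Brugada ECGs.
- **Study A:** say what the three categories are for this dataset, and report how many hold-out ECGs fall in each stratum.

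The cost is protocol wording and one normal/abnormal field in the expert read if it is not already recorded; Study A does not list the labels, so this cannot be assumed. NN3 will have fewer ECGs for training and testing, hence wider intervals, and its reported accuracy may be less favourable.
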